5.4 Adherence Assessment

For this study, adherence will be defined as 90% or greater compliance with prescribed regimen, based on pill counts (number of pills consumed/number of days since previous visit). Study drug intake compliance will be assessed by means of capsule count by a study team member at 30, 60, and 90-day visits. In order to encourage high levels of adherence, a member of the study team will call each participant on a biweekly basis to encourage continued adherence.

The gold standard for clinical trials is by intent-to-treat. An analysis of the prognostic significance of actual dose consumed over the active period has value, but a comparison with placebo is not recommended. This would be a secondary analysis and would allow for determination of whether higher consumption while on active medication resulted in greater changes to outcome variables. For this study, a completers analysis will be performed on the target population of older adults (age ≥ 65 years).

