9.3 Definition of Populations

Intent-to-treat population for the primary outcome is synonymous to those getting baseline and three-month biopsies, whether or not they adhere to the treatment. Every effort will be made to bring back participants for their three month (post-treatment) biopsy visit, regardless of their levels of adherence. Intent-to-treat for serial measurements will include those with at least one of their follow-up visits. As above, we shall make every effort to get all follow-up visits completed, regardless of adherence.

The per protocol (PP) population will consist of all patients in the ITT population who are not major protocol violators. Specifically, PP population will consist of individuals who did not take any prohibited therapies during the trial, had $\geq 90\%$ adherence with prescribed regimen based on pill counts, and completed all baseline and post-treatment assessments.

The gold standard for clinical trials is by intent-to-treat. An analysis of the prognostic significance of actual dose consumed over the active period has value since it will allow for further analysis of dose effects. This will be a secondary analysis, and will allow for determination of whether higher consumption while on active medication results in greater changes to outcome variables. For this study, a completer analysis will be performed on the target population of older adults (age \geq 65 years).

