9.4 Interim Analyses and Stopping Rules

No interim analyses are planned.

To determine the short and long term toxicities associated with administration of two doses of resveratrol when compared to a placebo in adults aged ≥ 65 years. The incidence, type, and severity of adverse events will be recorded during all phases of treatment and follow-up according to the Schedule of Activities shown in **Table 1**.

A single grade IV toxicity or two grade III toxicities will trigger an off cycle review by the DSMB, who can recommend suspension, amendment, or termination of the trial.

Toxicity due to this therapy is expected to be low. A description of each of the following study endpoints will be made at the conclusion of the subjects' accrual and 90 day post-treatment assessment:

- A. The number of subjects experiencing grades 1-5 adverse events according to Common Terminology Criteria for Adverse Events (CTCAE) v.3.0; the nature of these events; and the timing of their occurrence.
- B. The presence and magnitude of detectable change in blood chemistries.

Participants may have their treatment discontinued (permanently or temporarily) but remain on study for the following reasons; (a) unacceptable toxicity (≥ grade 3 toxicity) related to administration of resveratrol, using the toxicity criteria outlined in **Table 4**; (b) participant non-compliance with the study protocol; or (c) intercurrent disease, medication use, or condition that would affect the assessment of the participant's status. Of course, a participant is free to withdraw from the study at any time.

The study physician ([name]) will advise on whether or not he believes the participant should be removed or temporarily suspended from the study based on the toxicity criteria listed below.

Table 4. Dosage adjustment scheduled based on changes in blood chemistry values or participant report of clinically important symptoms.

Lab	Value	Placebo	Resveratrol 1000mg/day	Resveratrol 1500mg/day
WBC (n/μL)	< 3,000	Temporary Stop	Temporary Stop	Temporary Stop
Platelets (n/μL)	< 50,000	Temporary Stop	Temporary Stop	Temporary Stop
Creatinine Clearance (mL/min)	< 30	Temporary Stop	Temporary Stop	Temporary Stop
AST, ALT	> 2.0x ULN	Temporary Stop	Temporary Stop	Temporary Stop
Hematocrit	< 27%	Temporary Stop	Temporary Stop	Temporary Stop

Lab	Value	Placebo	Resveratrol 1000mg/day	Resveratrol 1500mg/day
Clinically Important Symptoms	Yes	Temporary Stop	Temporary Stop	Temporary Stop

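### The secondary analysis of actual dose consumed cannot determine a dose effect: within an arm, intake is post-randomisation behaviour, so report the result as an association and rest dose conclusions on the planned 1500 vs 1000 mg/day contrast

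*Combined protocol and SAP*

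**What the plan says.** Section 9.3 (Definition of Populations) says that an analysis of the actual dose consumed "has value since it will allow for further analysis of dose effects". It adds "This will be a secondary analysis", and that it "will allow for determination of whether higher consumption while on active medication results in greater changes to outcome variables". Section 5.4 (Adherence Assessment) makes the same claim in the conditional and adds one caution: "a comparison with placebo is not recommended".

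Intake comes from capsule counts. Section 5.4 defines it as "number of pills consumed/number of days since previous visit", so days off product lower it.

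Section 9.4 provides for interruptions: "Participants may have their treatment discontinued (permanently or temporarily) but remain on study for the following reasons", namely related toxicity, non-compliance, or intercurrent disease, medication use or condition. Table 4 in that section, headed "Dosage adjustment scheduled based on changes in blood chemistry values or participant report of clinically important symptoms", lists temporary stops, identical in all three arms.

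Section 9.3 defines the intent-to-treat population for the primary outcome as those with both biopsies, "whether or not they adhere to the treatment", and Section 9.2 seeks a follow-up biopsy even from people who stop the product. Participants with low intake can therefore contribute an outcome.

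Neither section gives a model, dose scale, arm term, covariates, analysis set or rule for stopped days, and neither mentions confounding among participants on active product.

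**The concern.** The randomised groups are comparable at baseline. People who take more or fewer capsules within one group need not be. Someone who feels unwell may skip capsules or be stopped under Section 9.4, and the same ill health may affect State 3 respiration at day 90. A regression of change on intake then picks up the health difference and presents it as the effect of more resveratrol.

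At stake is what the trial may conclude about dose. Read literally, Section 9.3 would let a significant intake slope be reported as evidence that more resveratrol produces more change, when an adherer effect alone could have produced it.

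**Working it through.** **1. The plan's own figures.** The plan states none for the consumption analysis. The nearest is in Section 9.2: with 18 completers per arm and a baseline-to-day-90 correlation of 0.7, 80% power for 0.81 SD pairwise and 0.69 SD for the primary contrast.

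- SD of change = √(2 × (1 − 0.7)) = 0.775 SD.
- Pairwise standard error = 0.775 × √(2/18) = 0.258. By noncentral t on 34 df, 80% power needs 0.745 SD, and 0.81 SD has 86% power.
- Primary contrast standard error = 0.775 × √(1/18 + 1/36) = 0.224. By noncentral t on 51 df, 80% power needs 0.639 SD, and 0.69 SD has 86% power.

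The stated pair fits a correlation of about 0.65 (0.690 and 0.804 SD). The figures are thus conservative, and the mismatch does not bear on this point.

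**2. Within-arm analysis when the drug has no effect.** Inputs from the plan: 18 completers per arm, so 36 on active product, and a two-sided 5% level. Assumed: a health factor correlates ρ with adherence and ρ with change. The induced correlation between intake and change is ρ². By Fisher z, the mean of the test statistic is atanh(ρ²) × √(36 − 3).

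| ρ | ρ² | atanh(ρ²) × √33 | False positives, Fisher z | Simulated, mg with arm term | Simulated, percent of capsules |
|---|---|---|---|---|---|
| 0.3 | 0.09 | 0.52 | 8% | 8% | 8% |
| 0.5 | 0.25 | 1.47 | 31% | 28% | 29% |
| 0.7 | 0.49 | 3.08 | 87% | 82% | 85% |

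The simulations used 20,000 trials per setting and an assumed adherence mean of 92% and SD of 10 points, capped at 100% (about 8 points after capping). With no confounding the rate was 5%. A separate simulation gave 27-29% with an arm term at ρ = 0.5.

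**3. Milligrams pooled over both active arms.** The 1000 vs 1500 difference is randomised and dilutes the bias. With mean adherence 0.90 (assumed) and adherence SD s:

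- self-selected variance = s² × (1000² + 1500²)/2 = s² × 1,625,000;
- randomised variance = 0.90² × 250² = 50,625.

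The self-selected share is 4,062.5/54,687.5 = 7% at s = 0.05, 16,250/66,875 = 24% at s = 0.10, and 65,000/115,625 = 56% at s = 0.20. Simulated false-positive rates on pooled milligrams, with the adherence of step 2, were 6%, 8% and 19% at ρ = 0.3, 0.5 and 0.7. With mean adherence 85% and SD 20 points before capping, they were 15% at ρ = 0.5 and 49% at ρ = 0.7.

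**4. Treatment stops alone** (no health factor; milligrams with an arm term; all inputs assumed; change in State 3 SD units).

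| Share stopped | Intake lost | Change in those stopped | False positives |
|---|---|---|---|
| 10% | 25 points | 0.5 SD worse | 11% |
| 10% | 25 points | 1.0 SD worse | 27% |
| 20% | 30 points | 0.5 SD worse | 21% |
| 20% | 30 points | 1.0 SD worse | 58% |
| 10% | 25 points | 0.5 SD better | 11%, nearly all in the negative direction |

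**5. The randomised alternative.** The 1500 vs 1000 mg/day Satterthwaite t-test held 4.8-5.2% in every no-effect scenario.

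**6. The placebo arm as a check.** At ρ = 0.5 the mean slope was 0.228 SD per 10 points of adherence on placebo and 0.224 on active, so the placebo arm shows the bias without bias of its own. With 18 people it reached p < 0.05 in only 16% of trials. Fisher z agrees: atanh(0.25) × √15 = 0.99, about 17%.

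**7. A 0/1000/1500 trend contrast.** Doses minus their mean of 833.3 give weights −5, 1, 4. Against the primary weights −2, 1, 1 at equal n, the correlation is (10 + 1 + 4)/√(42 × 6) = 15/15.87 = 0.945. If both active doses had the same 0.69 SD effect, this trend would be significant in 75% of trials (correlation 0.65) or 82% (0.7).

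**The case against.** The strongest case on the other side has four parts.

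- *Status.* The analysis is secondary, both sections call intent-to-treat the gold standard, and the text speaks of prognostic significance. This stands and limits the consequence. It does not cure the wording, since the same passages go on to promise a determination about dose.
- *Randomised evidence is already planned.* A reader might infer that the trial has no unconfounded dose comparison and needs a trend contrast over 0/1000/1500. The documents do not support this: Section 9.2 contrasts every pair of treatments, including 1500 vs 1000 mg/day. The trend would largely repeat the primary contrast and could be significant when the two active doses do not differ (step 7).
- *Intake is not wholly self-selected.* On pooled milligrams part of the variation is randomised, and the plan does not fix the scale. One might infer that the 27-31% rate describes the planned analysis. It describes one version of it. An arm term removes the randomised part and leaves the confounded part, so it is no remedy.
- *Stops may be rare.* Section 9.4 expects low toxicity, Table 4 treats all arms alike, and Section 5.4 plans biweekly adherence calls. One might infer that stops under Table 4 drive the bias or always push it upward. Neither follows: the pathway is small if toxicity is low, and its direction can reverse. Ordinary differences in adherence remain.

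A reader might also take the Section 5.4 caution as ruling out any use of the placebo arm. Its natural meaning is a sound warning against comparing intake-selected active participants with placebo. It does not address an intake slope within the placebo arm.

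**Conclusion.** The point holds as a limit on what the consumption analysis can conclude. Run as described, it can show a dose effect with no drug effect, and nothing in Sections 5.4 or 9.3 warns of this. Under assumed correlations of 0.5 the false-positive rate is about 8-15% on pooled milligrams and 27-31% within arm. At 0.3 with tight adherence it is about 5-8%.

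The correlations, adherence spread and stop rates are all assumptions. The figures show that a spurious result is possible. They do not predict its size or its sign in this trial. The primary contrast and the pairwise comparisons, which compare groups as randomised, are unaffected. The change is worth making because it is nearly free and alters what may be claimed about dose.

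**What to change.** 1. In Sections 5.4 and 9.3, replace the claim of determination with wording such as: *This exploratory analysis describes the association between the amount of product taken and change in outcome among participants on active product. It does not estimate the effect of dose.*
2. State in Section 9.3 that conclusions about more versus less active dose rest on the randomised 1500 vs 1000 mg/day Satterthwaite comparison in Section 9.2. Do not use the 0/1000/1500 trend contrast for this.
3. If the consumption analysis is kept, report the slope of change on percent of capsules taken within the active arms beside the same slope in the placebo arm, each as an estimate with a 95% confidence interval. State how stopped days count. Note that a non-significant placebo slope with about 18 participants does not rule out confounding.

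The cost is a few sentences in the plan and a few lines of code. The capsule counts and biopsies are already to be collected in all arms. The downside is a weaker claim from the consumption data.

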9.4 Interim Analyses and Stopping Rules

No interim analyses are planned.

To determine the short and long term toxicities associated with administration of two doses of resveratrol when compared to a placebo in adults aged ≥ 65 years. The incidence, type, and severity of adverse events will be recorded during all phases of treatment and follow-up according to the Schedule of Activities shown in **Table 1**.

A single grade IV toxicity or two grade III toxicities will trigger an off cycle review by the DSMB, who can recommend suspension, amendment, or termination of the trial.

Toxicity due to this therapy is expected to be low. A description of each of the following study endpoints will be made at the conclusion of the subjects' accrual and 90 day post-treatment assessment:

- A. The number of subjects experiencing grades 1-5 adverse events according to Common Terminology Criteria for Adverse Events (CTCAE) v.3.0; the nature of these events; and the timing of their occurrence.
- B. The presence and magnitude of detectable change in blood chemistries.

Participants may have their treatment discontinued (permanently or temporarily) but remain on study for the following reasons; (a) unacceptable toxicity (≥ grade 3 toxicity) related to administration of resveratrol, using the toxicity criteria outlined in **Table 4**; (b) participant non-compliance with the study protocol; or (c) intercurrent disease, medication use, or condition that would affect the assessment of the participant's status. Of course, a participant is free to withdraw from the study at any time.

The study physician ([name]) will advise on whether or not he believes the participant should be removed or temporarily suspended from the study based on the toxicity criteria listed below.

Table 4. Dosage adjustment scheduled based on changes in blood chemistry values or participant report of clinically important symptoms.

Lab	Value	Placebo	Resveratrol 1000mg/day	Resveratrol 1500mg/day
WBC (n/μL)	< 3,000	Temporary Stop	Temporary Stop	Temporary Stop
Platelets (n/μL)	< 50,000	Temporary Stop	Temporary Stop	Temporary Stop
Creatinine Clearance (mL/min)	< 30	Temporary Stop	Temporary Stop	Temporary Stop
AST, ALT	> 2.0x ULN	Temporary Stop	Temporary Stop	Temporary Stop
Hematocrit	< 27%	Temporary Stop	Temporary Stop	Temporary Stop

Lab	Value	Placebo	Resveratrol 1000mg/day	Resveratrol 1500mg/day
Clinically Important Symptoms	Yes	Temporary Stop	Temporary Stop	Temporary Stop

The oversight committee will review the number of intercurrent events by condition, and will determine if the statistician should review the events by condition and/or whether the blind should be broken. The statistician will then report the findings of these analyses to the oversight committee and NCCIH. Based on this information, the oversight committee, in conjunction with NCCIH, will determine whether the study should continue.

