3. STUDY DESIGN

The proposed study will utilize a double-blind, placebo controlled, parallel design to determine whether 90 days of resveratrol supplementation in older men and women (\geq 65 years) is associated with (i) increases in muscle mitochondrial respiration (state 3 and 4), (ii) increases in levels of PGC-1 α , AMP-activated protein kinase (AMPK), and sirtuins (SIRT1 and SIRT3), and (iii) improvements in functional performance and metabolic parameters. To achieve these aims, 60 participants will be randomized to receive a placebo (n=20), 1000 mg/day of resveratrol (n=20), or 1500 mg/day of resveratrol (n=20) for a 90-day period. We will collect muscle specimens from the vastus lateralis at baseline and after 90 days of intervention, for biochemical analyses (See **Table 1** for planned data collection and procedures). In addition to the measures listed in **Table 1**, we will also monitor blood chemistries every 30 days at monthly clinic visits. To enhance retention, participants will receive biweekly phone calls throughout the 90-day treatment period. Following the completion of this trial, one in-person follow-up assessment will be conducted at approximately 30 days post-treatment, to monitor blood chemistries and ascertain adverse events. In addition, approximately 10-days following muscle Biopsy procedure, a follow-up visit will take place to assure absence of biopsy complications and to monitor blood chemistries.

Importantly, previous data demonstrate that 30 days of supplementation is sufficient for detecting meaningful changes in muscle mitochondrial biomarkers and clinical parameters in obese middle-aged adults, as proposed in the current study;[41] however, we propose to extend the supplementation duration to 90 days and to recruit a mixed population of men and women with diverse functional status. The justification for this extension is two-fold: our selected participant sample is comprised of older adults, who have been found to have lower levels of mitochondrial function than younger adults, and The RIPE Trial, our pilot resveratrol study, showed increased mitochondrial activity, as well as improvements in cognitive function, following a 90-day intervention.

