For the Muscle Biopsy Visit in particular, we will employ strategies to ensure that participant discomfort is as low as possible and that this procedure goes smoothly. Although there are some risks associated with this procedure, including discomfort during the muscle biopsy procedure, scarring from the muscle biopsy skin incision, risk of bleeding, and risk of infection, we will do all we can to minimize these risks and thereby increase the likelihood the participant will return for a second muscle biopsy visit. First, as in previous studies conducted at our center, the muscle biopsy will be performed under sterile conditions using sterile technique. Second, local anesthesia will be used with topical lidocaine to minimize discomfort during the procedure. Third, [name], who will be the primary physician performing these biopsies, has extensive experience with this procedure and has performed muscle biopsies in multiple studies conducted over the past five years.

We will also provide compensation to participants for completing study visits, as described below. Participants will complete two Baseline Assessment visits, two visits during the study (day 30 and day 60), two Post-Treatment Assessment study visits, and two follow-up visits at 10 days and 30 days, following completion of the Post-Treatment muscle biopsy visit at clinic. To ensure health and safety after biopsy visit, participants will be contacted by telephone 24 hours after procedure, 3 – 5 days after procedure, and will attend an in-person visit 10 days after the procedure. Participants will receive \$75 in compensation for completion of the first Baseline Assessment visit,

and \$150 in compensation for completion of the second Baseline Assessment Visit (i.e., muscle biopsy visit). Participants will receive \$75 in compensation for completion of the first Post-Treatment Assessment visit, and \$150 in compensation for completion of the second Post-Treatment Assessment visit (i.e., muscle biopsy visit). Participants will also receive \$50 in compensation for completion of the day 10 visit, day 30 visit, and day 60 visit, as well as \$50 for completion of each of the two follow-up visits at 10 days and 30 days following completion of the second muscle biopsy visit.

Managing participants using prohibited medication/interventions after enrollment

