Risks associated with resveratrol supplementation: Toxicity from the doses of resveratrol used in this study is likely to be low based on animal studies, and doses of 1000 mg/day have been well tolerated in previous safety trials in young and middle-age adults.[58-60] Additionally, a recent repeated-dosing study found that a dose of 200 mg of resveratrol at eight hour intervals for a three day period was well tolerated in older adults (age $\geq 65 \text{ years}$),[61] and doses of 1000 mg/day, 1500 mg/day, and 2000 mg/day of resveratrol supplementation were well tolerated in older adults during a four week intervention.[56] Based on the findings described above, we have chosen the test doses of resveratrol chosen for the proposed study to be 1000 mg/day and 1500 mg/day. Adverse effects of resveratrol have not been reported at these doses; however, long-term side effects are not known. Resveratrol is structurally similar to the synthetic estrogen diethylstilbestrol, and may have estrogenic activity. Resveratrol might also interact with blood thinners such as warfarin, and non-steroidal anti-inflammatory medications, thereby increasing the risk for bleeding. In our resveratrol pilot study, *The RIPE Trial*, resveratrol supplementation at 1000 mg/day had minimal effects on blood chemistries, and there were no significant differences in the number of participants reporting adverse or toxic events (e.g. headaches) across the three conditions (all p values > 0.05).

Risk management in participants using prohibited medication/interventions after study enrollment.

If the participant reports any change in medications, this information will be recorded in the participant's file (i.e., source documents and case report forms). If a participant reports use of any prohibited interventions as listed below and in sections 5.3.3. of the protocol (Prohibited Interventions) post-randomization, the participant will be withdrawn from the study.

Prohibited Interventions

• Active treatment for cancer, stroke, peripheral vascular disease, coronary artery disease, myocardial infarction, congestive heart failure (stage III or IV), valvular

heart disease, major psychiatric disease, severe anemia, liver or renal disease, diabetes, severe osteoarthritis, blindness or deafness, fracture in upper or lower extremity, upper or lower extremity amputation, or Parkinson's disease; - Safety Reasons

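### Section 9.4 sets the safety description at the 90-day assessment, before the 10-day and 30-day follow-up visits, so the last participants enrolled could enter it with about 30 days less observation

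*Combined protocol and SAP*

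**What the plan says.** Section 9.4 names two safety endpoints: the number of participants with grade 1–5 events (with their nature and timing), and detectable change in blood chemistries. Both are to be described at the conclusion of "accrual and 90 day post-treatment assessment".

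Section 9.4 opens its safety text with the aim "To determine the short and long term toxicities associated with administration of two doses of resveratrol when compared to a placebo" and then says: "The incidence, type, and severity of adverse events will be recorded during all phases of treatment and follow-up".

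Section 4.3 lists the late visits as "two Post-Treatment Assessment study visits, and two follow-up visits at 10 days and 30 days, following completion of the Post-Treatment muscle biopsy visit". The post-treatment assessment and the follow-up visits are thus separate items, in that order. Section 9.3 likewise calls the three-month biopsy visit post-treatment.

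Section 6.2.5 has adverse events, CMP and CBC collected at both the 10-day and the 30-day follow-up visits, and makes the 30-day visit the last of the study. Section 3 gives the purpose of the visit about 30 days after treatment: "to monitor blood chemistries and ascertain adverse events".

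The only comparative safety method is one sentence at the end of Section 9.2, assigning side effects to Fisher's exact test. It gives no data cutoff. Section 9.3 defines intent-to-treat and per-protocol populations but no safety population or safety period.

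**The concern.** The plan collects safety data through the 30-day follow-up but ties the description of those data to an earlier milestone. Recording and summarising are different steps, and only the summarising step has a stated time. If that time is followed, some participants enter the safety table before their last two visits.

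Those visits matter for two reasons. They are the in-person checks after the second biopsy, and Section 7.1 lists bleeding and infection among the biopsy risks and says resveratrol may raise bleeding risk together with blood thinners or non-steroidal anti-inflammatory drugs. They also supply the blood results taken after the product is finished, which would show whether a laboratory change reverses or appears late.

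A smaller matter is the aim itself. Section 9.4 speaks of long-term toxicity, which the plan does not define, while the dosing is "or 1500 mg/day of resveratrol (n=20) for a 90-day period" and observation ends about 30 days later.

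**Working it through.** **1. What the milestone means.** The phrase in Section 9.4 can be read in two ways.
- The post-treatment assessment made at 90 days. This matches the use of the term in Sections 4.3 and 9.3.
- An assessment 90 days after treatment ends. No such visit is scheduled; the last is the 30-day follow-up.

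Only the first reading fits the schedule.

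**2. Visit calendar.** Inputs, with Baseline Visit 2 (randomization and first dispensing) as day 0:
- 90-Day Visit 1: day 90 (nominal)
- 90-Day Visit 2 (biopsy): 0 to 7 days after Visit 1 (Section 6.2.5)
- 10-day follow-up: 10 ± 3 days after Visit 2 (Section 6.2.5)
- 30-day follow-up: 20 ± 7 days after the 10-day follow-up (Section 6.2.5)

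The plan's own figure first: 10 + 20 = 30 days after Visit 2. This reproduces the roughly 30 days stated in Section 3, give or take the week allowed between the two 90-day visits.

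| Visit | Nominal day |
|---|---|
| 90-Day Visit 1 | 90 |
| 90-Day Visit 2 | 90 + 0 to 90 + 7 = 90–97 |
| 10-day follow-up | 90 + 10 to 97 + 10 = 100–107 |
| 30-day follow-up | 100 + 20 to 107 + 20 = 120–127 |

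With the windows, the 30-day follow-up falls between (10 − 3) + (20 − 7) = 20 and (10 + 3) + (20 + 7) = 40 days after Visit 2. If 90-Day Visit 1 is assumed to fall at day 90 ± 7, the last visit falls between 83 + 0 + 20 = day 103 and 97 + 7 + 40 = day 144.

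**3. What a participant contributes at the milestone.**
- Both follow-up visits pending: about 90–97 days
- 10-day visit done, 30-day visit pending: about 100–107 days
- Both done: about 120–127 days

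The shortfall for a participant with both pending is 120 − 90 = 127 − 97 = 30 days and two visits, each with adverse-event collection and a CMP/CBC draw.

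**4. How many participants are affected.** The milestone is a date for the whole trial. Those affected are the participants whose 90-Day Visit 2 fell within about 30 days (20 to 40 with the windows) before it. If all 60 were enrolled evenly over A days and none dropped out, that is about 60 × 30 / A = 1,800 / A participants. The documents do not give A, so the count cannot be fixed, but it is confined to the end of the enrolment sequence.

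**5. Whether another section supplies a later cutoff.** The Fisher's exact sentence in Section 9.2 has none. Section 7.5 follows reported events until resolved or stable, but this concerns events already reported. Sections 7.4 and 7.6 provide bi-annual and annual reports for oversight; they do not set the data cutoff for the final description.

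**The case against.** The best reply is that Section 9.4 says when a report is written, not which data enter it. Events are recorded through follow-up, the timing of events is part of the first endpoint, and nothing excludes follow-up data. By the end of accrual and the last 90-day assessment, most participants may have finished follow-up. This stands. It rules out the inference that every participant loses the follow-up period or that the trial discards a fixed share of its safety data.

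A reader might also infer that complications of the second biopsy fall wholly outside the description. The documents do not support that. The biopsy takes place at 90-Day Visit 2, which belongs to the post-treatment assessment. Adverse events are assessed at that visit, and Appendix 1 has reactions during and after the procedure recorded. Section 4.3 adds telephone contact at 24 hours and at 3–5 days. What is exposed is delayed complications, in participants with visits still pending.

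The visit vocabulary is also loose: Sections 9.5.1 and 9.5.2 call the 90-day biopsy visit the second follow-up visit. That weakens a strict reading but does not supply a later cutoff.

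On *long term*, the phrase is an undefined aim. A reader might take it as a claim that the trial will establish long-term safety, but no such result is stated, and Section 7.1 says openly that "long-term side effects are not known".

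Finally, randomization uses permuted blocks, so the last participants enrolled should be spread across the arms. A shortened observation period is therefore more likely to lose information than to tilt the comparison.

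**Conclusion.** The point holds as a misplaced milestone, not as a demonstrated loss of data. Section 9.4 names a time for the safety description that precedes two visits at which safety data are collected, and no other section moves it. Followed as written, participants with both visits pending would contribute about 90–97 days rather than about 120–127, so length of observation would depend on enrolment order.

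This rests on three assumptions: that *post-treatment* means the 90-day visits, as in Sections 4.3 and 9.3; that visits fall at their nominal times; and that the description is made at the stated milestone and not updated. The number of participants affected depends on the pace of enrolment, which the documents do not give. Sample size, power, the error rate and the primary analysis are untouched.

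The *long term* wording is minor. That about 120–127 days is too short for the term is a reasonable judgement rather than something a figure in the documents proves.

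**What to change.** - In Section 9.4, state that the description of adverse events and blood chemistries is made after the last participant's Follow-Up 30 Day visit and uses all adverse events and laboratory results through that visit.
- In Section 9.2, give the Fisher's exact comparison of side effects the same cutoff.
- Show the on-product and follow-up periods separately, and state the date that divides them (for example the last capsule taken), because the second biopsy may fall up to a week after 90-Day Visit 1.
- In Section 9.4, define *long term*, or replace it with the period observed: 90 days of product plus about 30 days.

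The cost is a few sentences and a safety table about a month later. No visit, sample or participant is added.
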